Participants assigned to receive WASABI will complete at least 3 EMA sessions per week, 1 hour of digitally delivered Cognitive Behavioral Group Therapy (dCBGT) per week, and weekly cognitive biases assessments and self-reports for 12 weeks. During the intervention, these participants will also have daily access to 1:1 and group chat Instant Messaging (IM) and may have weekly electronic check-ins with Site Study personnel (as needed). Participants in the control condition will be asked to attend 1 hour of digitally delivered Cognitive Behavioral Group Therapy (dCBGT) per week for 12 weeks and may have weekly electronic check-ins with Site Study personnel (as needed).

For each arm, as soon as 3-6 participants have completed the baseline assessments and randomization, a cohort will be assembled. The Study Coordinator will meet with the participants to orient them to the study platforms and the WASABI Clinician will meet with each participant individually for a brief introduction and orientation prior to the 12-week intervention and will review of the *Procedures and Guidelines to Group Therapy*. The WASABI Coordinator and/or Clinician will create a virtual support group open only to cohort participants. The WASABI Clinician will explain her role, make group introductions, and will invite participants to attend weekly 1-hour group sessions (dCBGT+ WASABI or dCBGT only, depending on the treatment arm). For the treatment group (dCBGT + WASABI), between group sessions, the WASABI Clinician will spend approximately 30 min/day keeping the chat active during work hours, checking it approximately 3 times a day and may respond to messages participants leave, as appropriate. The WASABI Coordinator will be included in the support group chat and may monitor the chat content, and may be active in the chat in the absence of the WASABI Clinician.

Participants will be re-evaluated again at the expected time of completion, immediately following the 12-week intervention, to evaluate changes in performance. Finally, participants will be asked to fill out an online exit survey to rate enjoyment, usability, perceived benefits, and ease of fit into schedule.

The protocol will be conducted in accordance with the protocol submitted to and approved by the reviewing Institutional Review Board and approval will be obtained prior to implementation.

Study Population

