completing their study activities. Participants that do not have a compatible personal device, do not wish to use their personal device, or do not agree to configure their settings and download the necessary application(s) for program use will be loaned a mobile device for the duration of the *Intervention and Program Use* period. Participants will be asked to sign a form acknowledging they have been loaned a study device. The research team may attempt to complete this visit on the same day as *Baseline Assessment (V1)*, but a separate visit may be scheduled, if necessary.

Duration: ~30-60 minutes remotely or in-person at the Study Site.

6. *Intervention and Program Use*: Participants will have a 1:1 orientation with the WASABI Clinician prior to engaging in their assigned group intervention activities. Site Study personnel will review the *Procedures and Guidelines to Group Therapy* and will ask the parent/legal guardian and/or participant to review and sign this form. After which, participants will remotely engage in the intervention for 12 weeks, completing approximately 12 hours of dCBGT in addition to other assigned study activities.
7. *Post-Intervention Assessment (End of Study Visit; V3)*: After the *Intervention and Program Use* period is completed, the participant will be asked to complete their final assessment visit, where they'll repeat all assessments performed at baseline to assess changes in performance.

Duration: ~2 hours remotely or in-person at the Study Site.

Participants expressing interest in returning their device to its original settings will be instructed by Site Study personnel on how to delete study application(s) during this visit or at the time of study exit. Participants loaned a study device will be asked to return the loaned device at this visit.

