This study employs two mobile-device delivered interventions: the treatment intervention (dCBGT+WASABI) and an active control (dCBGT). Participants will be asked to use their assigned program activities over the course of the 12-week *Intervention and Program Use* period. Participants will be asked to complete 12 weekly 1-hour group sessions (dCBGT) led by a Site Study Clinician (WASABI Clinician). Participants assigned to the treatment intervention (WASABI) will be asked to complete at least 3 EMA sessions per week and weekly cognitive assessments, in addition to dCBGT. Several elements of flexibility are allowed in the schedule to accommodate the challenges that adolescents with Social Anxiety may face:

- *Location of Use:* Some participants may experience barriers to receiving treatment, including geographic location, availability of trained therapists, long waiting lists, and the requirement to take time off from school for clinic visits. This intervention is a remote intervention that allows participants to access the intervention and program activities remotely. Every effort will be made to schedule the weekly group therapy sessions at a time that is most convenient for the participant. EMAs and weekly cognitive assessments are mobile-accessible, allowing participants to complete them at different locations, as convenient.
- *Variable Number of Total Sessions:* Given fatigue (common in this population), commitments to non-study activities, health issues and/or re-integration into school, work and home life, we expect that some participants will not be able to complete the weekly dCBGT sessions for 12 weeks. To accommodate this, we will be understanding of their circumstances, recommend that participants complete as many sessions as their schedule permits, and explain that the results of the trial may benefit from frequent and consistent involvement in group sessions. Similarly, participants granted access to daily EMAs and weekly cognitive assessments will be encouraged to complete at least 3

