standard application (BrainHQ) on an Internet-connected iOS device and goes to a general log-in screen. The participant then logs into the experimental treatment program platform through the BrainHQ application (using a study provided username that contains no personally identifiable information). Participants are directed to their assigned EMAs, cognitive biases assessments, or self-report questionnaire and perform their assigned activities over the course of a session.

Participant will use Google Meet and Chat, a HIPAA-compliant videoconferencing and instant messaging application on an Internet-connected iOS mobile device and goes to a general log-in screen. The participant then logs in using a study provided account. Participants assigned to the WASABI are expected to join 12, 1 hour-long dCBGT sessions using the Google Meet application. These will be scheduled and facilitated by the WASABI Clinician.

Active Control Program (dCBGT): Given the nature of the augmentation study, it's expected that participants in the control condition may spend less time, overall, on study activities as compared to the *Experimental Treatment Intervention* (dCBGT+WASABI). In an effort to equate time spent in the intervention and control for the effects of mobile device use, contact with personnel, monetary payments, and nonspecific engagement, participants in the control condition will be asked to attend 12 weekly, 1-hour, group dCBGT sessions and complete "homework" associated with traditional dCBGT.

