G-Suite Google Chat and Meet: This platform allows participants to communicate with others via the app without having to share their full name, mobile phone number or email to do so. Participants also have the opportunity to personalize their profile, by entering a short bio and a picture of their choice. In order to access the Google Meet and Chat apps, participants will have a unique username/login that contains no personally identifiable information. Once logged in, they will be operating within the Google Meet and Chat HIPAA-compliant digital environment, and data that are produced, transmitted, and shared among users will be exclusively visible/readable to the research participants and authorized University of Minnesota and Posit Science staff. These data will include personally identifiable information—such as faces, first names or aliases, biographical and medical information—similar to what happens during all in-person group therapy sessions. The Google Meet and Chat API will allow participants to exchange end-to-end encrypted instant and group messages, as well as make end-to-end encrypted group voice and video calls. Participants will be aware that research team members at the University of Minnesota and Posit Science will have access to the group chat history and will be monitoring its contents throughout the intervention period. As such, participant are informed that any personally identifying information voluntarily shared on this platform will be viewed by staff at both the University of Minnesota and Posit Science. Google Meet and Chat use end-to-end encryption for voice and video calls, as well as instant messages. Google Meet and Chat's voice calls are encrypted with DTLS and SRTP, its video calls with RTP, and its instant messages with RTP. In addition to this, client-server communication is protected by Transport Layer Security. More information about how Google Meet and Chat protects privacy can be found here: <https://support.google.com/a/answer/3407054>

Participants assigned to the Active Control condition will not be asked to use the Google Chat app, as it is unique to the WASABI intervention. Participants in both groups will be able to download other Google apps associated with their deidentified study assigned G-Suite account, such as Google Calendar and Gmail, to facilitate communication with the Site Study team and

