- *Risks of Email Communication:* This study will rely on the use of email communication between Site Study personnel and research participants as part of their participation in the intervention. Site Study personnel may expect to email participants about their upcoming appointments, provide weekly updates on program usage, or communicate other important study information. Participants may also ask questions of Site Study personnel using email. There are risks associated with email communication, and these risks increase when emails are sent without an encryption service. Risks of sending or receiving unencrypted emails include, but are not limited to:
 - Others can intercept messages
 - If messages are sent or received on an employer-owned device, the employer may have the right to save and read the messages. The internet or cell-phone provider may also have the right to save and read email messages
 - A copy of the message may be saved on a device or computer system, even if it is deleted
 - If an email address is not typed correctly, it can be sent to the wrong person
 - Emails can spread computer viruses
 - Others may be able to access messages on devices that were lost, stolen, or thrown away
 - If a participant changes emails without notifying study personnel, they may miss communications.

Participants will be encouraged to report any adverse effects occurring during the duration of the study to the Site Study point of contact.

PSC does not provide compensation for research-related injuries and will not reimburse or pay medical expenses for the treatment of research-related injuries.

Although there is little chance for a study-related emergency, Site Investigators and Site Study

personnel are required to following institutional standard operating procedures for obtaining emergency care or treatment for adverse effects requiring such. This study has adequate personnel and equipment to respond to expected adverse effects, and maintains working knowledge of the nearest treatment facilities available to patients enrolled into this study.

Potential Benefits

Two levels of benefit will be described to participants:

1. Benefit to Science: Results from this study will directly benefit the applied science in social anxiety disorders. Understanding if the scientific design principles of WASABI drive superior outcomes to current evidence-based treatments will provide considerable insight to scientists and clinicians working in social anxiety disorders.

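### The control arm matches dCBGT sessions and payments but not staff contact or device use as the Protocol states, so the comparison tests the WASABI package, not its design features

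*Protocol*

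**What the plan says.** The Protocol section on the active control program begins with a concession: "it's expected that participants in the control condition may spend less time, overall, on study activities". The next sentence gives the purpose of the control activities: "In an effort to equate time spent in the intervention and control for the effects of mobile device use, contact with personnel", with payments and non-specific engagement added to the list. It then names the means: "participants in the control condition will be asked to attend 12 weekly, 1-hour, group dCBGT sessions", together with the usual dCBGT homework. Later in the same section the control is said to match the experimental program on session intensity, attendance time, overall engagement and expectation, and to differ by lacking the WASABI adjunct.

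The sessions are common to both arms. The description of protocol devices says: "Participants will be asked to complete 12 weekly 1-hour group sessions (dCBGT) led by a Site Study Clinician".

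Other activities are not common. For the treatment group, General Study Design says that "the WASABI Clinician will spend approximately 30 min/day keeping the chat active during work hours". The description of the experimental intervention adds clinician messaging triggered by alerts, three EMA sessions a week, and weekly SPAI-B and cognitive-bias assessments. On the control side, Application Security says: "Participants assigned to the Active Control condition will not be asked to use the Google Chat app, as it is unique to the WASABI intervention". Controls open the BrainHQ app for two embedded assessment sessions, one before and one after the intervention.

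On interpretation, Potential Benefits lists as the gain to science: "Understanding if the scientific design principles of WASABI drive superior outcomes to current evidence-based treatments". Data Analysis hypothesises that WASABI's innovative features improve treatment delivery and carry-over of skills to daily life.

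**The concern.** The means named for equating the arms is twelve group sessions plus homework. Both arms receive these, so they cannot offset something that only one arm receives. The Protocol therefore claims a property for its control that its own schedule does not provide.

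What is at stake is the reading of a difference on the secondary outcomes (LSAS-CA, SPAI, MASC-2, SSQ, ASSES). A reader who accepts that contact and device use are controlled will credit such a difference to the closed loop, the EMA-based personalisation or the design principles. Added clinician attention, peer chat or time on the app could produce the same difference. Sample Size Justification says that p < 0.05 would support a statement that the intervention improves social anxiety, and that the data will be used to power the Phase II trial. A misdescribed control would carry over into that case.

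**Working it through.** **The plan's own figure.** 12 sessions × 1 h = 12 h, which agrees with Study Procedures: "completing approximately 12 hours of dCBGT in addition to other assigned study activities". This holds in both arms.

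**Inputs**
- Group session: 1 h a week for 12 weeks, both arms (description of protocol devices).
- Clinician chat time: about 0.5 h a day per cohort, WASABI arm only (General Study Design).
- Chat days per week, d: not stated. The reference to work hours suggests 5; I assume 5 and show 3 to 7.
- Cohort size, c: 3 to 6 (General Study Design).
- EMA: at least 3 sessions a week, WASABI arm only.
- Control app use: two embedded sessions, no chat.

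**Scheduled clinician time per cohort over 12 weeks** = 12 × (1 + 0.5d); control = 12 × 1 = 12 h.

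| d | WASABI cohort | Ratio to control |
|---|---|---|
| 3 | 12 × 2.5 = 30 h | 2.5 |
| 5 | 12 × 3.5 = 42 h | 3.5 |
| 7 | 12 × 4.5 = 54 h | 4.5 |

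**Share per participant.** The table measures clinician effort for a cohort, not contact received by one person. Credit each member with the full group hour and an equal share of the chat time, so extra time = 0.5d / c hours a week.
- d = 5, c = 6: 2.5 / 6 = 0.417 h, or 25 min; ratio (1 + 0.417) / 1 = 1.42.
- d = 5, c = 3: 2.5 / 3 = 0.833 h, or 50 min; ratio 1.83.
- Extremes: d = 3, c = 6 gives 1 + 1.5 / 6 = 1.25; d = 7, c = 3 gives 1 + 3.5 / 3 = 2.17.

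**What these figures leave out.** Alert responses and dashboard review occur only in the WASABI arm and have no stated hours, so they are not counted. In the other direction, the 30 minutes include checking the chat about three times a day and replying as appropriate, so not all of it is contact delivered. Orientation and as-needed check-ins are offered to both arms and are left out of both sides.

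**Device use.** EMA: 3 × 12 = at least 36 sessions against 0. SPAI-B and bias tasks: weekly for 12 weeks plus before and after, against two sessions. Controls also use an iOS device for their 12 h of video sessions, so their device use is not nil; it is matched only for those hours.

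**Summary**

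| Matched | Not matched |
|---|---|
| Number and length of dCBGT sessions | Daily clinician chat and peer chat |
| Assignment of homework | Alert-driven messaging |
| Orientation, as-needed check-ins | EMA sessions, weekly app tasks |
| Payments | Personalisation of sessions and homework from EMA data |

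**The case against.** The strongest reply is that clinician and peer messaging is part of the treatment and not a confounder. Background describes WASABI as cueing peers and providers to connect by message, the experimental intervention lists messaging as one of its three treatment tools, and the control section defines the contrast as dCBGT without the adjunct. In an add-on design, that contrast validly estimates the package. This stands. A reader might infer that a difference could not be credited to WASABI at all. The documents do not support that, because an effect that came through contact would still be an effect of a declared component.

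A reader might also take the 3.5-fold ratio as contact received by each participant. It is not: it is cohort-level clinician effort and depends on an unstated five-day week.

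Three further replies have some force. The wording expresses an effort, and it follows directly on the concession about time. Overall engagement can be read as engagement with dCBGT only. The sentence about design principles is a statement of benefit, whereas the decision sentence in Sample Size Justification refers to the intervention as a whole. These replies soften the claim but do not remove it: staff contact and device use are named as factors being controlled for, and the activities offered for that purpose add nothing beyond what both arms already have.

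Finally, the consequence is limited. The SAP's primary outcomes are feasibility measures in the WASABI arm, analysed descriptively. The Protocol concedes that it lacks power for an augmentation effect, and the SAP gives less weight to hypothesis tests.

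**Conclusion.** The inconsistency is real and minor. The stated control for staff contact, device use and overall engagement is not delivered by the schedule, which makes all three unequal by design. Scheduled clinician time per cohort is 30 to 54 h against 12 h for 3 to 7 chat days a week. Per participant, at 5 days, it is about 1.4 to 1.8 times control (1.25 to 2.17 over the whole range of days and cohort sizes). These figures rest on the assumed chat days, an equal split of chat time and full credit for the group hour. None of them gives parity.

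The trial can estimate the effect of dCBGT plus the whole WASABI package, including its added clinician and peer contact, against dCBGT alone. It cannot apportion an effect between the closed loop or other specific features and the added attention, chat and device time. The feasibility conclusions are unaffected.

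**What to change.** In the active control section, replace the statements on equating or controlling for contact, device use and overall engagement with a plain list: dCBGT sessions, homework and payments are matched; clinician and peer messaging, EMA and weekly app tasks are not.

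In Data Analysis and Potential Benefits, state that any secondary-outcome difference is attributed to the whole package, including its added clinician and peer contact, and not to specific design principles.

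Beside the effect estimates, report by arm the sessions attended, group-chat and 1:1 messages, and app use already recorded, with check-ins where they were recorded. Keep this table descriptive. Contact arises after randomisation and is part of the package, so adjusting for it could remove part of the effect.

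The cost is a change of wording and one table. Session attendance, group messages and EMA completion are already outcomes, and chat history and app usage are already held; counts of 1:1 messages and check-ins may be less complete. No trial procedure or sample size changes. The SAP is partly in the past tense, so conduct may be over; in that case the same wording and table belong in the report. The downside for the sponsor is a narrower claim.

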We hypothesize that the innovative features of WASABI will improve the quality of treatment delivery and facilitate the generalization of trained skills into real-world settings. The measures collected to determine the efficacy of the program for this trial are clinical ratings of anxiety and social anxiety symptoms (LSAS-CA), self-report inventories of social anxiety symptoms (SPAI), broad measures of anxiety (MASC-2), self-report inventories of social skills (SSQ), and self-report inventories of social functioning (ASSES). To test this hypothesis, we will use a linear mixed model approach. We will first compare treatment and active control groups in the ITT population to determine if any differences in baseline demographic, characterization, outcomes variables, or total program use time remain after the randomization process. Any such factors that show trend level significant differences ($p < 0.1$) will be noted and used as covariates in the linear mixed model analysis. The criterion for statistical significance is $p < 0.05$. Results with $p < 0.1$ will be described as trends.

Performance on the attention bias and interpretation bias assessments will be modeled longitudinally to examine if these measures can serve as potential moderators and mediators. To test if the attenuation of attention and interpretation biases mediates improvements in outcome measures, we will use repeated-measures linear mixed modeling to test in the active group the effects of WASABI on LSAS-CA, SPAI, SSQ and ASSES, and then model outcomes as a function of performance improvements on the attention bias and interpretation bias assessments.

Because we are interested in examining the ecological validity of WASABI, we will not restrict the analyses only to participants who adhered to all intervention requirements. Within-group effect sizes (Cohen's d) will be computed using the mean change scores (post-intervention minus baseline) and the change score SDs.

These measures will be analyzed to power the pivotal study proposed for Phase II. For the FDA, we will collect data documenting that WASABI meets its design requirements when used in the field by clinicians and patients, and that clinicians deem its risk/benefit ratio as acceptable and view it as adequate/appropriate for the target population.

Data Management

Data collected in this study may include paper forms for consent/assent forms and some assessments from clinician- or psychometrician-administered structured interviews, neuropsychological or functional assessments. Other assessments will be administered remotely and collected electronically through REDCap servers (hosted on HIPAA compliant UMN servers) or the program platform (hosted on Posit Science servers). Fully executed consent/assent forms completed by Site Study personnel and securely stored at the Study Site will not be shared with Posit Science. With the exception of dates that assessments are completed, personally identifying information collected by UMN Site Study personnel will not be collected or stored with study assessment or performance data on the BrainHQ app on Posit Science Servers and will not be shared with Posit Science. Personally identifying information voluntarily disclosed by participants on BrainHQ (EMA questionnaires) and the Google Meet and Chat platforms during the intervention will be accessible to the Posit Science research team. Participants are informed that both the UMN and Posit Science research teams will be monitoring their chat history on the Google Meet and Chat platforms. Prior to entering the participant's study record, direct identifiers (names, email addresses) will be redacted. De-identified, study-related data collected on paper and shared with Posit Science will be recorded into a secure, web-based electronic case report form (eCRF). This system meets all relevant privacy and security standards for electronic clinical trial data entry and storage, as well as the Health Insurance Portability and Accountability Act (HIPAA) standards for confidentiality and privacy.

Following consent, each participant will be assigned a standardized Participant Identification Number (PIDN) composed of digits to identify the study and 3 digits to identify the participant. The digits will begin with "001" for the first consented participant and ascend thereafter. All eCRF data entry will be de-identified, using the PIDN only and not the participant name, but will include the date of the assessment administration.

Study personnel will transcribe and upload de-identified data and de-identified source documentation into the study database for the purpose of data monitoring. PSC data entry personnel and Site Study personnel will interact frequently throughout the study to accomplish the quality goals of the data management process through the below process.

Participants may email Site Study personnel with questions or concerns, or to make arrangements for study visits. If deemed significant and relevant to the participant's study record, de-identified emails may be saved to the participant's study file. To de-identify emails, all direct identifiers (name, email address, date of birth, etc.) will be redacted from the email in PDF format. Site Study personnel will place black bars over any directly identifying information. The redaction will be verified by a secondary staff member for accuracy and completion to ensure patient privacy prior to being uploaded for permanent storage at the Site and shared with Posit Science. The dates of communication will be maintained in the emails to provide context for the conversation.

Periodic analysis of the data will be performed in order to examine the expected distributions of data, and to identify outliers for possible data mistakes. PSC data management personnel and Site Study personnel will interact frequently throughout the study to accomplish the quality goals of the data management process through the below process.

Periodic analysis of each data field (across all cases) will be performed in order to examine the expected distributions of data, and to identify outliers for possible data mistakes. Particular attention will be paid to the following:

- *Data Cleaning:* All eCRFs are automatically reviewed to check for omitted data and data inconsistencies. These deficiencies are required to be resolved at the point of data entry to prevent errors from entering the system.
- *Data Editing:* Each data record is evaluated on a regular interval. Any discovered error is then referred to the clinical site Investigator Designee within the Electronic Data Management (eCRF) System via the Data Monitor. The Investigator Designee will review the queries and make the corrections through the eCRF system. All such changes are automatically logged to allow a complete audit trail and recovery to any point in the change log if required.
- *Data Update:* The cycle of data editing will be ongoing until all the data are clean. If further data entry or source documentation errors are discovered during review, the corrections will be made at that time through the eCRF system.
- *Data Back-up:* The eCRF system employs an automatic continuous replication system to ensure that all data including change logs and access logs are replicated to two independent remote servers. At any point, the system is capable of emitting the entire store of eCRFs as paper CRFs for offsite storage or auditing if required.

We will take all standard and appropriate steps to protect the privacy and confidentiality of participants in this trial. At enrollment participants will be assigned a PIDN as described above, and all study data collection derived from that participant will be coded by PIDN. All

eCRF pages, including those with demographic as well as assessment data, will have the PIDN on them rather than the participants name. No personally identifying information will be shared with Posit Science, with the exception of dates that assessments are completed and date of birth. However, personally identifying information voluntarily disclosed by participants on the BrainHQ (EMA questionnaires) and Google Meet and Chat platforms during the intervention will be accessible to the Posit Science research team. Prior to entering the participant's study record, direct identifiers (names, email addresses) will be redacted. Accurate and complete study records will be maintained and stored in a confidential manner so as to protect the confidentiality of participant information.

The eCRF system runs on remote servers not physically accessible to any study staff (including PSC staff); all electronic access to the eCRF system is logged and regularly reviewed for any inappropriate access. All study related paper materials will be stored in locked file cabinets inside of locked rooms when not in use. During remote procedures, study personnel may shred the original paper documents after Posit Science has completed the data monitoring and reconciliation process and approved shredding of documents. Until documents are ready for shredding, they will be stored by the respective study personnel with limited access until the documents are shred or transferred to the Study Site. All participant use of the BrainHQ program will use a login based on the PIDN, and study programs will not collect or store any personally identifiable information, with the exception of any volunteered information included in EMA questionnaires, on the laptop or on PSC servers, with the exception of dates that assessments are completion. Participants will choose whether to use their first name or an alias for the Google Meet account.

We note this protocol does collect sensitive information, i.e. when assessing suicidal ideation, that may result in a reporting requirement to state or local authorities. The Study Site is expected to follow standard institutional policies in such cases to ensure the protection of participants and proper reporting. If Site Study personnel become aware of specific issues outside of the ordinary data collection procedures (e.g., child abuse) they will follow established institutional procedures already in place as appropriate for their local jurisdiction to report such knowledge.

Confidentiality

Participation in research may involve a potential loss of privacy. All records and documents pertaining to participation in this study will be handled as confidentially as possible. However, absolute confidentiality cannot be guaranteed.

All information, if collected on paper, will be kept in areas of limited access available to approved study personnel only. Any physical records will be maintained in locked cabinets in locked offices, until the appropriate time at which documents may be shredded. Access to these cabinets will be limited to the study team. During remote procedures, study personnel may shred the original paper documents after Posit Science has completed the data monitoring and reconciliation process and approved shredding of documents. Until documents are ready for shredding, they will be stored by the respective study personnel with limited access until the documents are shred or transferred to the Study Site.

Electronic data will be password protected and securely stored. The servers maintained by both Posit Science and UMN are HIPAA compliant, secure servers, that will require permissions from the study team to access.

Absolute confidentiality in therapy groups is difficult to achieve irrespective of the delivery method (in-person, video-conference, etc.), as there is no guarantee that other group members will maintain confidentiality about sensitive information. However, in order to decrease the likelihood of breaches of confidentiality among group members, we will 1) provide informed consent about confidentiality; 2) educate group members about confidentiality; and 3) make the discussion of confidentiality an ongoing process.

- First, study participants will learn about confidentiality during the informed consent process. The consent form will clearly describe the roles and responsibilities of all parties and the limits of confidentiality.
- Second, individual sessions will be held between the Site Study Coordinator and/or WASABI Clinician and each participant to educate them regarding confidentiality prior to entering the intervention. Participants will be informed that 1) they have the right to choose an alias rather than their first name and decide at any point what information they choose to disclose; 2) the WASABI Clinician will respect the patients' ability to choose what they disclose, and keep the promises of faithfulness and loyalty to all participants, including not revealing information participants disclose; 3) the WASABI Clinician cannot promise that other group members will maintain confidentiality; 4) the WASABI Clinician may have a legal obligation to break confidentiality in certain circumstances (e.g., child abuse), and those circumstances will be fully explained. The WASABI Clinician will follow established procedures appropriate for their local jurisdiction to report such knowledge; 5) the UMN and Posit Science research teams will be monitoring the BrainHQ (EMA questionnaires) and Google Meet and Chat contents, including chat history, throughout the intervention and as such any volunteered information that may be personally identifying will be available to both UMN and Posit Science monitors.

- Third, participants will be asked to read, sign and agree to be bound by a modified version of the American Psychological Association procedures and guidelines for group therapy (<http://www.apadivisions.org/division-49/publications/newsletter/group-psychologist/2011/04/group-procedures.aspx>), adapted for the target population, while in the intervention.
- Finally, during the first group therapy session, the WASABI clinician will encourage group members to embrace the concept of confidentiality, making it their own rather than a mandatory rule.

Given that one of the goals of WASABI is to enhance social functioning in people with social anxiety, we will not discourage group members from sharing contact information and befriending other study participants. Research shows that peer-to-peer interactions occur naturally on social media platforms and serve many purposes, such as establishing new relationships, maintaining relationships, reconnecting with people, disclosing personal experiences of living with social anxiety, seeking and sharing information related to symptoms and medications.

Representatives of the Sponsor, the reviewing Institutional Review Board, and the National Institute on Aging will be permitted to audit study-related data and related materials. Personally identifiable information will not be used in any study reports or publications; data contained in these will only be presented or published in aggregate form.

Disposition of Data

The following study records will be retained by the Study Site for minimum of two years following the conclusion of the study:

1. signed participant informed consent forms (securely held at UMN and stored with limited access),
2. patient medical records, including all significant diagnostic reports,
3. supporting documentation of all adverse events,
4. completed eCRFs, and;
5. study related correspondence and study reports.

Paper records from this study must be stored in locked areas of limited access. During remote procedures, documents will be stored by the respective study personnel in a safe location with limited access until the documents can be shredded or transferred to the Study Site. Electronic data must be securely held with restricted access available to personnel on a need-to-know

basis only. Google Team Drive access will be restricted to authorized study personnel by invitation only.

Research staff will comply with the requirements of UMN (i.e., the enrolling institution) data storage and disposition policies at the conclusion of the record retention period.

Sharing Research Results

Overall study results will be available to participants through ClinicalTrials.gov and when such results are completed and accepted for publication. At enrollment, information is collected that, if appropriate, we will share with the participant to ensure they are receiving appropriate health care (i.e. suicidality) as assessed by the C-SSRS. Any participant presenting a safety concern for any of these medical issues will be referred to ensure they are receiving appropriate treatment. We do not intend to share individual assessment data with participants, as the assessment battery is not intended to be the type of comprehensive battery a rehabilitation psychologist would use to guide treatment. Any participant interested in such comprehensive assessment will be referred to an appropriate clinician.

Foreseeable Risks, Risk Management & Emergency Response

